**Exact time points of blood draws may be modified based on interim PK assessment (from this study).**

Per individual, the trial-related blood loss (including any losses in the maneuver) will not exceed 3% of the total blood volume and will not exceed 1% at any single time (see Section 12.2). The total volume of blood is estimated at 80 to 90 mL/kg body weight; 3% is 2.4 mL blood per kg body weight.

### **7.1.3.2.3 Blood Collection for Plasma Levels of Tedizolid Phosphate and Tedizolid**

Sample collection, storage and shipment instructions for plasma samples to evaluate the PK of tedizolid phosphate and its active metabolite, tedizolid, will be provided in the Laboratory Manual. Results of analysis will be reported separately.

### **7.1.4 Other Procedures**

#### **7.1.4.1 Withdrawal/Discontinuation**

Subjects who discontinue/withdraw from treatment prior to completion of the treatment regimen (eg, stop midway through an IV infusion) should be encouraged to continue to be followed for all remaining study visits.

When a subject discontinues/withdraws from participation in the trial, all applicable activities scheduled for the final trial visit should be performed at the time of discontinuation. Any adverse events which are present at the time of discontinuation/withdrawal should be followed in accordance with the safety requirements outlined in Section 7.2 - Assessing and Recording Adverse Events.

#### **7.1.4.2 Blinding/Unblinding**

This is an open label trial; there is no blinding for this trial.

Section 5.8 outlines the criteria for allowing subjects who are discontinued from treatment to continue to be monitored in the trial.

#### **7.1.4.3 Calibration of Critical Equipment**

The investigator or qualified designee has the responsibility to ensure that any critical device or instrument used for a clinical evaluation/test during a clinical trial that provides important information about inclusion/exclusion criteria and/or safety or efficacy parameters shall be suitably calibrated and maintained to ensure that the data obtained is reliable and/or reproducible. Documentation of equipment calibration must be retained as source documentation at the trial site.

Critical Equipment for this trial includes:

- Drug storage thermometer (which should have high/low recording)
- Local laboratory analytical instruments
- Sphygmomanometer
- Infusion pump

### **7.1.5 Visit Requirements**

Visit requirements are outlined in Section 6.0 - Trial Flow Chart. Specific procedure-related details are provided above in Section 7.1 - Trial Procedures.

#### **7.1.5.1 Screening Visit**

Within 4 days (inclusive, Day -3 to Day 1) prior to treatment allocation, potential subjects will be evaluated to determine that they fulfill the entry requirements as set forth in Section 5.1. Age eligibility will be assessed at the Screening Visit. Screening procedures may be repeated after consultation with the Sponsor. If a subject is rescreened, screening procedures should be repeated, unless they fall within the window specified. A subject may be rescreened only 1 time; age eligibility will be determined at rescreening.

#### **7.1.5.2 Treatment Period Visits**

Details of allocation to treatment (IV or oral) and PK sampling scheme are provided in Section 5.3. Details about the PK sampling schemes are provided in Section 7.1.3.2.2.

Details of blood sampling, processing, handling, and processing procedures will be provided in the Laboratory Manual.

#### **7.1.5.3 Discontinued Subjects Continuing to be Monitored in the Trial**

Subjects who discontinue treatment (including subjects who discontinue from study drug partway through an infusion) should have all safety assessments (including clinical safety labs, vital signs, physical examination, and collection of adverse events and medical history) completed as per Section 6.0, but do not need to have PK sampling performed. This is also true of subjects who “spit up” the oral dose.

Subjects who discontinue from the study prior to receiving a dose of treatment (eg, due to removal of consent by the parent or LAR, or due to an emergent condition or circumstance which, in the opinion of the investigator or sponsor, places the subject at unnecessary risk through continued participation, or does not allow adherence to the protocol) do not need to conduct further visits or assessments.

#### **7.1.5.4 Post-Trial**

The Post-treatment Follow-up Contact will be a follow-up assessment performed by telephone contact at least 14 days after administration of trial drug to determine if any adverse events have occurred since the previous visit.

The Follow-up Contact should be conducted in person if there are ongoing adverse events or clinically important laboratory abnormalities that require follow-up.

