Estimated duration of trial	
The Sponsor estimates that the trial will require approximately 3 years from the time the documented informed consent is provided for the first subject until the last subject's last study-related phone call or visit.
 
For purposes of analysis and reporting, the overall study ends when the Sponsor receives the last laboratory result or at the time of final contact with the last participant, whichever comes last.

Duration of Participation	Each subject will participate in the trial for approximately 18-20 days from the time the parent, guardian, or legally acceptable representative provides the documented informed consent form (ICF) through the final contact (Day 14). After a screening phase of $\leq 4$ days, each subject will receive tedizolid phosphate as a single-dose or as multiple doses (twice daily for 3 days). After dosing is complete, each subject will be followed for 14 days for adverse events.

A list of abbreviations used in this document can be found in Section 12.4.

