## 6.0 TRIAL FLOW CHART

Trial Period:	Screening	Treatment		Post-treatment
	1 Screening	2 Allocation & Treatment	3 Day 2-3 Visit	Follow-up Telephone Contact a
Visit Number/Title:				
Scheduled Day (single-dose)	-3 to 1 b	1	2	14
Scheduled Day (multiple-dose)	-3 to 1 b	1	2 – 3 c	17
Scheduling Window (Days):				14-21
Administrative Procedures				
Informed Consent (before any trial-related procedures/assessments)	X			
Inclusion/Exclusion Criteria	X			
Subject Identification Card	X	X		
Medical History	X			
Prior and Concomitant Medication Review	X	X	X	X
Treatment Allocation		X		
Tedizolid Phosphate (MK-1986) Administration d		X	X c	
Clinical Procedures/Assessments				
Full Physical Examination	X			
Directed Physical Examination		X	X	
Height	X			
Weight	X			
Electrocardiogram (5-, 12-, or 15-lead) e	X			
Vital Signs (respiratory rate, BP, HR, temperature) f,g	X	X	X	
Adverse Events Monitoring	X	X	X	X

Trial Period:	Screening	Treatment		Post-treatment
Visit Number/Title:	1 Screening	2 Allocation & Treatment	3 Day 2-3 Visit	Follow-up Telephone Contact a
Scheduled Day (single-dose)	-3 to 1 b	1	2	14
Scheduled Day (multiple-dose)	-3 to 1 b	1	2 – 3 c	17
Scheduling Window (Days):				14-21
Laboratory Procedures/Assessments				
Hematology Laboratory Tests h	X		X	
Blood Chemistry Laboratory Tests h	X		X	
Blood Samples for PK Analysis i		X i	X i	
Urinalysis	X			

Abbreviations: AE=adverse event; BP=blood pressure; ECG=electrocardiogram; HR=heart rate; IV=intravenous; PK=pharmacokinetics

- a. The Post-treatment Follow-up Contact should be conducted in person if there are ongoing adverse events or clinically important laboratory abnormalities that require follow-up.
- b. Screening procedures may be completed on Day 1. The screening window is up to 3 calendar days prior to treatment allocation.
- c. Subjects assigned to receive multiple doses of IV tedizolid phosphate will receive study drug on Days 2 and 3. Study medication (single- or multiple-dose) will be dispensed once only from IRT. For multiple-dose subjects, the only study procedure on Day 2 is administration of study drug; all clinical and laboratory study procedures specified in the Trial Flow Chart (eg, hematology, chemistry, etc.) and administration of study drug should be performed on Day 3.

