All adverse events that occur after the participant's legally authorized representative provides documented informed consent but before treatment allocation/randomization must be reported by the investigator if they cause the subject to be excluded from the trial, or are the result of a protocol-specified intervention, including but not limited to washout or discontinuation of usual therapy, diet, placebo treatment or a procedure. From the time of treatment allocation/randomization through 14 days following cessation of treatment, all adverse events must be reported by the investigator. Such events will be recorded at each examination on the Adverse Event case report forms/worksheets. The reporting timeframe for adverse events meeting any serious criteria is described in Section 7.2.2.1. The investigator will make every attempt to follow all subjects with non-serious adverse events for outcome.

Electronic reporting procedures can be found in the Electronic Data Capture (EDC) data entry guidelines. Paper reporting procedures can be found in the Investigator Trial File Binder (or equivalent).

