## **7.2.2 Immediate Reporting of Adverse Events to the Sponsor**

### **7.2.2.1 Serious Adverse Events**

A serious adverse event is any adverse event occurring at any dose or during any use of Sponsor's product that:

- Results in death;
- Is life threatening;
- Results in persistent or significant disability/incapacity;
- Results in or prolongs an existing inpatient hospitalization;
- Is a congenital anomaly/birth defect;
- Is an other important medical event.

**Note:** In addition to the above criteria, adverse events meeting either of the below criteria, although not serious per ICH definition, are reportable to the Sponsor in the same timeframe as SAEs to meet certain local requirements.

- Is a cancer;
- Is associated with an overdose.

Refer to [Table 5](#) for additional details regarding each of the above criteria.

For the time period beginning after documented informed consent is provided until treatment allocation/randomization, any serious adverse event, or follow up to a serious adverse event, including death due to any cause, that occurs to any subject must be reported within 24 hours to the Sponsor if it causes the subject to be excluded from the trial, or is the result of a protocol-specified intervention, including but not limited to washout or discontinuation of usual therapy, diet, placebo treatment or a procedure.

For the time period beginning at treatment allocation/randomization through 14 days following cessation of treatment, any serious adverse event, or follow up to a serious adverse event, including death due to any cause, whether or not related to the Sponsor's product, must be reported within 24 hours to the Sponsor either by electronic media or paper. Electronic reporting procedures can be found in the EDC data entry guidelines. Paper reporting procedures can be found in the Investigator Trial File Binder (or equivalent).

Additionally, any serious adverse event, considered by an investigator who is a qualified physician to be related to the Sponsor's product that is brought to the attention of the investigator at any time outside of the time period specified in the previous paragraph also must be reported immediately to the Sponsor.

All subjects with serious adverse events must be followed up for outcome.

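### The single-dose follow-up contact on Day 14 falls one day short of the protocol's own 14-day adverse-event period, and the shared 14-21 window has no stated anchor

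*Combined protocol and SAP*

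**What the plan says.** Four parts of the combined protocol and SAP set the end of safety follow-up.

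- **Section 7.1.5.4** describes the last contact as a "telephone contact at least 14 days after administration of trial drug to determine if any adverse events have occurred since the previous visit".
- **Section 7.2** sets the reporting period: "From the time of treatment allocation/randomization through 14 days following cessation of treatment, all adverse events must be reported by the investigator". Section 7.2.2.1 uses the same period for serious events ("For the time period beginning at treatment allocation/randomization through 14 days following cessation of treatment, any serious adverse event"), and Section 7.2.2.2 uses it for events of clinical interest.
- **Section 6.0** gives the schedule. The single-dose row reads "Scheduled Day (single-dose) -3 to 1 b 1 2 14", so the dose is on Day 1 and the contact on Day 14. The multiple-dose row reads "Scheduled Day (multiple-dose) -3 to 1 b 1 2 – 3 c 17", so the contact is on Day 17; footnote c places the later doses on Days 2 and 3. The row "Scheduling Window (Days" has a single entry, 14-21, for both regimens, and no footnote says what those days are counted from.
- **Section 1.0** says each subject takes part "through the final contact (Day 14", with no separate day for multiple-dose subjects. The same entry promises 14 days of adverse-event follow-up once dosing is complete.

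**The concern.** In the flow chart this contact is the only planned adverse-event assessment after the Day 2-3 visit. If it is made before the 14-day period is over, no later contact is planned that would prompt a report of an event in the last day or days.

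Safety and tolerability are the secondary objective in both parts of the trial. The multiple-dose neonatal cohorts are the newest exposure, and Section 2.1 says they open as of Amendment 05, so the schedule still governs subjects to be enrolled. The mismatch also leaves a site unable to tell whether a given contact is on time or a protocol deviation.

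**Working it through.** **Inputs.** Last dosing day: Day 1 for single-dose subjects and Day 3 for multiple-dose subjects (Section 6.0 and its footnote c). Scheduled contact: Day 14 and Day 17 (Section 6.0). Window: 14-21, anchor not stated (Section 6.0). Required interval: 14 days (Sections 7.1.5.4, 7.2, 7.2.2.1 and 7.2.2.2).

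**Step 1: scheduled days.** Days after last dose = contact day − last dosing day.

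- Single-dose: 14 − 1 = 13 days, one short. The earliest day that complies is 1 + 14 = Day 15.
- Multiple-dose: 17 − 3 = 14 days, which complies. The earliest day that complies is 3 + 14 = Day 17.

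**Step 2: can a counting convention reproduce both stated days?** Counting elapsed days gives Day 15 and Day 17. Counting the last dosing day as day one of the 14 gives Day 14 and Day 16. The flow chart states Day 14 and Day 17, so neither convention gives both. Day 17 fits only the elapsed count, and by that count the single-dose day is one short.

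**Step 3: the 14-21 window under each anchor.** Figures in brackets are days after the last dose.

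| Window counted as | Single-dose | Multiple-dose | Scheduled day inside the window? |
|---|---|---|---|
| Study days | Days 14-21 (13-20) | Days 14-21 (11-18) | Yes for both |
| Days after last dose | Days 15-22 (14-21) | Days 17-24 (14-21) | Day 14 no; Day 17 yes |
| Days after first dose | Days 15-22 (14-21) | Days 15-22 (12-19) | Day 14 no; Day 17 yes |

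Read as study days, only Day 14 fails for single-dose subjects (Days 15-21 comply), and Days 14-16 fail for multiple-dose subjects (Days 17-21 comply). No anchor makes the scheduled days, the window and the 14-day rule all agree.

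**Step 4: size.** Single-dose at the scheduled day: 14 − 13 = 1 day, and 1/14 = 7%. Multiple-dose at the earliest contact under the study-day reading: 14 − 11 = 3 days, and 3/14 = 21%.

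**Step 5: Section 1.0.** A Day 14 final contact for a multiple-dose subject conflicts with Day 17 in the flow chart. It also gives 14 − 3 = 11 days after the last dose, against the 14 days promised in the same entry.

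**The case against.** A reader might infer that the contact cannot meet the 14-day period at all. The documents do not support that. Day 17 is exactly 14 days after Day 3. Single-dose contacts on Days 15-21 comply under the study-day reading. If the window counts from the last dose, which fits Sections 7.1.5.4 and 7.2 best, every contact inside it complies for both regimens. A site that follows Section 7.1.5.4 can satisfy both the rule and the window.

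A reader might also infer that the call closes adverse-event collection. It does not. The investigator's duty runs to 14 days after treatment stops whenever the call is made, related serious events are reportable at any time, and ongoing events call for an in-person contact. What is lost is only a planned prompt.

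The 21% should not be read as expected loss. It needs the study-day reading and also a call three days before the scheduled Day 17, against Section 7.1.5.4. Nor do the scheduled days treat the regimens very differently: 13 days against 14.

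The consequences are small. The study is descriptive, its primary objectives are pharmacokinetic, and only 4 + 4 = 8 multiple-dose subjects are planned. Section 4.1.1 gives a terminal half-life of 12 hours in a paragraph on adult data; on that figure 13 days is 13 × 24 / 12 = 26 half-lives. The documents give no neonatal value.

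All of this stands and limits the size of the point. It does not remove the contradiction: a site that calls a single-dose subject exactly on the scheduled day departs from Section 7.1.5.4.

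**Conclusion.** The point holds as a minor inconsistency that affects conduct. A single-dose contact on the scheduled Day 14 is one day short of the period the protocol sets. The multiple-dose scheduled day is sound, but the unanchored window may permit an earlier call, with a conditional maximum of 3 of 14 days not covered. Section 1.0 contradicts the flow chart for multiple-dose subjects.

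The effect is confined to how completely events in the last one to three days of safety follow-up are elicited. The primary pharmacokinetic analysis is unaffected. The documents do not say on which days contacts are actually made, so the figures describe what the schedule permits, not what will be missed.

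The finding that Day 17 complies assumes the last dose is on Day 3, as footnote c implies. Six doses 12 hours apart span 5 × 12 = 60 hours (55 to 65 with the one-hour tolerance on each interval). At exact 12-hour intervals, a first dose after midday on Day 1 would carry the sixth into Day 4, and Day 17 would then be 13 days later. Counting from the actual last dose avoids that case too.

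**What to change.** Reconcile Sections 1.0, 6.0, 7.1.5.4 and 7.2. For both regimens, state the scheduled contact and its window in days after the last dose, so that neither falls before the end of the 14-day reporting period the protocol already sets. In Section 1.0, replace the single Day 14 with the same definition. In Section 7.1.5.4, make clear that the interval runs from the last dose.

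With the last dose on Day 1 or Day 3, the earliest contact becomes Day 15 for single-dose and Day 17 for multiple-dose subjects. If 14-21 is kept and counted from the last dose, the windows are Days 15-22 and Days 17-24.

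The cost is a wording change in the flow chart and the summary, with no new procedure or blood draw. The scheduled single-dose call moves by one day. The multiple-dose scheduled day does not move; only its earliest permitted call may, by up to three days.

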### **7.2 Assessing and Recording Adverse Events**

An adverse event is defined as any untoward medical occurrence in a patient or clinical investigation subject administered a pharmaceutical product and which does not necessarily have to have a causal relationship with this treatment. An adverse event can therefore be any unfavourable and unintended sign (including an abnormal laboratory finding, for example), symptom, or disease temporally associated with the use of a medicinal product or protocol-

specified procedure, whether or not considered related to the medicinal product or protocol-specified procedure. Any worsening (i.e., any clinically significant adverse change in frequency and/or intensity) of a preexisting condition that is temporally associated with the use of the Sponsor's product, is also an adverse event.

Changes resulting from normal growth and development that do not vary significantly in frequency or severity from expected levels are not to be considered adverse events. Examples of this may include, but are not limited to, teething, typical crying in infants and children and onset of menses or menopause occurring at a physiologically appropriate time.

Sponsor's product includes any pharmaceutical product, biological product, device, diagnostic agent or protocol-specified procedure, whether investigational (including placebo or active comparator medication) or marketed, manufactured by, licensed by, provided by or distributed by the Sponsor for human use.

Adverse events may occur during clinical trials, or as prescribed in clinical practice, from overdose (whether accidental or intentional), from abuse and from withdrawal.

All adverse events that occur after the participant's legally authorized representative provides documented informed consent but before treatment allocation/randomization must be reported by the investigator if they cause the subject to be excluded from the trial, or are the result of a protocol-specified intervention, including but not limited to washout or discontinuation of usual therapy, diet, placebo treatment or a procedure. From the time of treatment allocation/randomization through 14 days following cessation of treatment, all adverse events must be reported by the investigator. Such events will be recorded at each examination on the Adverse Event case report forms/worksheets. The reporting timeframe for adverse events meeting any serious criteria is described in Section 7.2.2.1. The investigator will make every attempt to follow all subjects with non-serious adverse events for outcome.

Electronic reporting procedures can be found in the Electronic Data Capture (EDC) data entry guidelines. Paper reporting procedures can be found in the Investigator Trial File Binder (or equivalent).

### **7.2.1 Definition of an Overdose for This Protocol and Reporting of Overdose to the Sponsor**

In this trial, an overdose is any dose higher than 1.25 times the protocol-specified dose of tedizolid phosphate. This threshold was selected conservatively, as on a dosage expected to produce an exposure (AUC) that matches the exposure reached at the no-observable-adverse-effect level in juvenile rats after 6 weeks of dosing (rats dosed from postnatal Day 7 through 56).

If an adverse event(s) is associated with ("results from") the overdose of Sponsor's product or vaccine, the adverse event(s) is reported as a non-serious adverse event, unless other serious criteria are met.

If a dose of Sponsor's product or vaccine meeting the protocol definition of overdose is taken without any associated clinical symptoms or abnormal laboratory results, the overdose is reported as a non-serious adverse event, using the terminology "accidental or intentional overdose without adverse effect."

All reports of overdose with and without an adverse event must be reported by the investigator within 24 hours to the Sponsor either by electronic media or paper. Electronic reporting procedures can be found in the EDC data entry guidelines. Paper reporting procedures can be found in the Investigator Trial File Binder (or equivalent).

## **7.2.2 Immediate Reporting of Adverse Events to the Sponsor**

### **7.2.2.1 Serious Adverse Events**

A serious adverse event is any adverse event occurring at any dose or during any use of Sponsor's product that:

- Results in death;
- Is life threatening;
- Results in persistent or significant disability/incapacity;
- Results in or prolongs an existing inpatient hospitalization;
- Is a congenital anomaly/birth defect;
- Is an other important medical event.

**Note:** In addition to the above criteria, adverse events meeting either of the below criteria, although not serious per ICH definition, are reportable to the Sponsor in the same timeframe as SAEs to meet certain local requirements.

- Is a cancer;
- Is associated with an overdose.

Refer to [Table 5](#) for additional details regarding each of the above criteria.

For the time period beginning after documented informed consent is provided until treatment allocation/randomization, any serious adverse event, or follow up to a serious adverse event, including death due to any cause, that occurs to any subject must be reported within 24 hours to the Sponsor if it causes the subject to be excluded from the trial, or is the result of a protocol-specified intervention, including but not limited to washout or discontinuation of usual therapy, diet, placebo treatment or a procedure.

For the time period beginning at treatment allocation/randomization through 14 days following cessation of treatment, any serious adverse event, or follow up to a serious adverse event, including death due to any cause, whether or not related to the Sponsor's product, must be reported within 24 hours to the Sponsor either by electronic media or paper. Electronic reporting procedures can be found in the EDC data entry guidelines. Paper reporting procedures can be found in the Investigator Trial File Binder (or equivalent).

Additionally, any serious adverse event, considered by an investigator who is a qualified physician to be related to the Sponsor's product that is brought to the attention of the investigator at any time outside of the time period specified in the previous paragraph also must be reported immediately to the Sponsor.

All subjects with serious adverse events must be followed up for outcome.

